FDAC case data will be retrieved directly from CJI following the development of a data sharing agreement. This data sharing agreement should be sufficient to enable access to all necessary FDAC data for the purposes of the study. Alternatively, however, separate data sharing agreements may have to be drawn for each of the individual FDAC sites. Further data sharing agreements will also be drawn for each of the participating Local Authorities in order to grant access to the necessary control case data.

Design

Table 2 Study design

² Note that this refers to RQ1, 2, 4 and 5. RQ3 draws on data from a prior cohort of FDAC participants (2017 and 2018).

³ Previously this was January 2021 – we expanded the date range to maximise sample size.

⁴ Manchester was the only Local Authority that agreed to provide non-FDAC care proceeding as usual data without an FDAC site in their area.

Study type and number of arms		Quasi-experimental design: Coarsened Exact Matching
Unit of identification		Case, parent, and child
Matching variables		Parent demographics, Domestic Violence, Alcohol or drug misuse, Child demographics, Case characteristics (see Table 3).
Primary outcome	variable	Reunification
	measure (instrument, scale)	Binary indicator derived from the placement of the child at the end of care proceedings.
Secondary outcomes	variables	
 1) Alcohol and drug misuse cessation; 2) Contested final hearing; and 3) Use of expert witnesses.
	measures (instrument, scale)	
 1) Binary indicator of whether the parent's alcohol and/or drug misuse has ceased; 2) Binary indicator of whether the final hearing was contested; 3) a) Binary indicator of whether expert witnesses were used during care proceedings; and b) Count of the number of different types of expert witness (based on the binary expert reports/assessments indicators, e.g. independent social work assessment, psychiatric assessment).

A randomised controlled trial was considered for this evaluation but was rejected as the judiciary thought that randomisation of families in care-proceedings could be subject to legal challenge. A feasibility study was conducted as part of this evaluation considering suitable evaluations. The impact evaluation, therefore, uses a quasi-experimental design: Coarsened Exact Matching (CEM).

Identification strategy

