The intervention group will consist of cases that have been selected by an FDAC site to receive FDAC care proceedings. A control group will be selected from non-FDAC cases that meet the basic criteria for inclusion in an FDAC but were not selected for FDAC. The basic criteria for inclusion in FDAC are that care proceedings have been issued and that there are concerns about parental alcohol or drug misuse as part of the care proceedings case. The average treatment effect will be estimated by combining a CEM approach, as described by lacus et al. (2009), with regression analysis.

Implementing CEM requires data for characteristics associated with selection into the intervention or the outcome at the start of care proceedings (see Table 3 for a list of all variables used to implement matching). For example, this could include risks to the child (such as parental alcohol or drug misuse or domestic violence in the household). Variables will be “coarsened” into binary or categorical variables (for example, if it is a continuous variable, such as the age of the child, the variable would be re-categorised into age bands). Some variables that are already collected in FDAC sites are currently collected categorically and will not require coarsening.

However, due to resourcing constraints faced by the Local Authorities, some variables collected ordinarily in FDAC cases will require recoding to be comparable to those in non-FDAC cases. For example, parental alcohol and drug misuse at the start of proceedings are assessed using clinical judgement (high, medium and low risk). Substance misuse is recorded differently by Local Authorities for non-FDAC cases, which only comprise types of parental substance misuse rather than clinical judgement of severity. Therefore, to be comparable to non-FDAC cases, severity of parental alcohol and drug misuse at the start of proceedings in FDAC cases will be recoded as general type of parental substance misuse (i.e. Drugs, Alcohol, Drugs and Alcohol, None, and Unknown). The recoded variable will then not require coarsening. Table 3 outlines the variables collected and how they will be coarsened for matching. A sensitivity analysis will test the impact of further collapsing coarsened variables.

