Local Authorities will be asked to complete this template using data from their own case management systems and case notes. Due to resourcing constraints faced by the Local Authorities, and following consultation, we removed some covariates from the planned analysis and data collection template. The original set of covariates can be found in Appendix C .

Table 3. Intended variables for matching intervention and control cases and coarsening strategy for child, parent and case-level outcomes			
Characteristics	Variable	Type	Coarsening Strategy
Child-level outcome: reunification			
Case characteristics	Date of issue	Date	Year and quarter
Parent characteristics	Primary carer – Age	Continuous	Age bands: Less than 18 years old, 18–24, 25–34, 35–44, 45 or older
	Primary carer – Gender	Categorical	No coarsening: Male, Female, Other, Unknown
	Primary carer – Ethnicity	Categorical	No coarsening: White, Asian/Asian British, Black African/Black Caribbean/Black British, Mixed/multiple ethnic groups, other, unknown
	Primary carer for how many children	Continuous	Bands: 0 (if not primary carer), 1, 2, 3 or more
	Primary carer – Age of youngest child cared for	Continuous	Age bands: Less than 12 months old, 1, 2–3, 4–7, 8–11, 12–16
	Primary carer – Past experience of domestic abuse	Categorical	No coarsening: Yes – perpetrator, Yes – Victim, Yes – both, No, Unknown
	Primary carer – Currently experiencing domestic abuse	Categorical	No coarsening: Yes – perpetrator, Yes – Victim, Yes – both, No, Unknown
	Primary carer – Whether misusing at time of referral	Categorical	No coarsening: Yes, No, Unknown

	Primary carer - Substance misuse type	Categorical	No coarsening: Drugs, Alcohol, Drugs and Alcohol, None, Unknown
Parent characteristics aggregated to case level	Number of parents in the case	Categorical	One, two three or more
Child characteristics	Age	Continuous	Age bands: Less than 12 months old, 1, 2-3, 4-7, 8-11, 12-16
	Gender	Categorical	No coarsening: Male, Female, Other, Unknown
	Ethnicity	Categorical	No coarsening: White, Asian/Asian British, Black African/Black Caribbean/Black British, Mixed/multiple ethnic groups, other, unknown
Parent-level outcome: substance misuse cessation			
Case characteristics	Date of issue	Date	Year and quarter
Parent characteristics	Age	Continuous	Age bands: Less than 18 years old, 18-24, 25-34, 35-44, 45 or older
	Gender	Categorical	No coarsening: Male, Female, Other, Unknown

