The primary outcome of interest will be a binary indicator of reunification immediately at the end of care proceedings. We define reunification as the legal order given for the child to either return to live with the parent, or to continue to live with the parent. Reunification is not achieved where the placement of a child at the end of care proceedings is different from the start of proceedings. This includes placement with another parent or family member at the end of care proceedings. For FDAC cases, the judge's ruling on the placement of the child will be recorded in the FDAC tool by FDAC staff. We expect the placement of the child would be recorded by Local Authorities and this will be captured in the data collection template for non-FDAC cases.

The secondary outcomes are parental alcohol and drug misuse cessation, whether the final hearing is contested, and whether expert witnesses were used during care proceedings.

Parental alcohol and drug misuse are currently recorded in the FDAC data tool as two key categorical variables: the severity of parental substance misuse (low, medium, high) and the level of risk to the child from parental substance misuse (low, borderline, harmful). This will be recorded differently in the new tool – using a suite of binary indicators that used to be fed into the clinical judgement that is currently used, due to resource constraints with non-FDAC data. The outcome variable will be a binary indicator of whether the parent is currently misusing drugs and/or alcohol at the end of care proceedings (where one indicates they are currently misusing and zero indicates they are not currently misusing).

As we are interested in the impact of FDAC on the likelihood of final care proceedings hearings being contested relative to non-FDAC care proceedings as usual (RQ4), contested final hearings will be recorded as a binary outcome. The final hearing will be classified as contested regardless of which party contests the hearing.

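### The child's placement at the start of proceedings is neither matched on nor adjusted for, although the primary outcome pools children who return to the parent with children who stay

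*Supplement*

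**What the plan says.** All references are to version 2.0 of the protocol (1 November 2022).

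- **Criterion for matching variables** (Identification strategy): "Implementing CEM requires data for characteristics associated with selection into the intervention or the outcome at the start of care proceedings". The same sentence presents Table 3 as complete: "see Table 3 for a list of all variables used to implement matching".
- **Child-level list** (Table 3): date of issue; nine primary-carer items (age, gender, ethnicity, number of children cared for, age of the youngest, past and current domestic abuse, misuse at referral, substance type); number of parents in the case; and the child's age, gender and ethnicity. That makes 14 variables. None records where the child was living, or under what legal status, at issue.
- **Regression** (Analysis plan, Primary Analysis): the covariates are the same matching variables in uncoarsened form, with random intercepts for carer, case and site.
- **Outcome definition** (Outcome measures): "We define reunification as the legal order given for the child to either return to live with the parent, or to continue to live with" that parent. The next sentence reads "Reunification is not achieved where the placement of a child at the end of care proceedings is different from the start of proceedings".
- **Outcome measure** (Table 2): "Binary indicator derived from the placement of the child at the end of care proceedings".
- **Expected selection** (Participants): sites apply their own and partly subjective criteria, and the plan expects systematic differences between the groups.

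**The concern.** A child at home when proceedings are issued and a child already removed start from different places with respect to this outcome. One needs the arrangement to hold; the other needs it to be reversed. If FDAC sites take a different mix of the two from the comparison Local Authorities, the difference in mix enters the FDAC estimate as though it were an effect.

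The plan's own criterion would bring start placement into Table 3, and nothing else in the design makes up for its absence. Double robustness protects against misspecifying one of two models, not against leaving the same confounder out of both. Hedges' g and L1 are computed on the listed covariates only. The sensitivity analyses drop covariates or collapse categories; none adds start placement.

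**Working it through.** **1. Does coding the outcome need start placement?** The statements side by side:

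| Start → end | Definition (return or continue) | Rule comparing end with start, read literally | Table 2 (end placement) |
|---|---|---|---|
| With parent → with same parent | reunified | not excluded | reunified |
| Away → with parent | reunified | not reunified | reunified |
| With parent → away | not reunified | not reunified | not reunified |

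The second row is a contradiction within Outcome measures. Only the comparison rule needs start placement; the definition and Table 2 can be applied from the final order. Start placement matters on either reading. Under the literal rule a child away at issue cannot be coded as reunified at all. Under the other reading the outcome mixes two starting states.

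**2. The plan's detectable effect.** Inputs from Minimum detectable effect size calculations and Table 5: ICC 0.70; R² 0.20 at level one and 0.10 at level two; 430 cases; 1.4 children per case; control rate 25%; two-sided alpha 0.05; power 0.80; equal groups, so P(1−P) = 0.25.

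- Variance term: 0.70 × 0.90 / (0.25 × 430) + 0.30 × 0.80 / (0.25 × 430 × 1.4) = 0.005860 + 0.001595 = 0.007455
- MDES = (1.960 + 0.842) × √0.007455 = 0.242
- OR = exp(0.2419 × π/√3) = 1.551
- RRR = 1.551 / (0.75 + 0.25 × 1.551) = 1.363
- Difference = 25 × 0.363 = 9.1 points

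This agrees with the stated 1.36 and 9.1. It uses the level-two R² on the ICC term and an exponential for the odds ratio. Appendix F as printed puts the level-one R² on the ICC term, which gives 1.351 and 8.8 points even with the exponential.

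**3. Illustrative bias.** With no true effect, spurious risk difference = (difference between arms in the share at home at issue, remaining after matching) × (gap in reunification probability between children at home and away). The documents supply neither factor. Two assumed gaps, each consistent with 25% overall:

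- 45% against 12% (gap 33 points), with 39.4% at home: 0.394 × 0.45 + 0.606 × 0.12 = 0.250
- 60% against 15% (gap 45 points), with 22.2% at home: 0.222 × 0.60 + 0.778 × 0.15 = 0.250

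| Residual imbalance | Gap 33 points | Gap 45 points |
|---|---|---|
| 10 points | 3.3 points, RR 28.3/25 = 1.13 | 4.5 points, RR 29.5/25 = 1.18 |
| 20 points | 6.6 points, RR 31.6/25 = 1.26 | 9.0 points, RR 34.0/25 = 1.36 |

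Over a wider assumed range (imbalance 5 to 30 points, gap 10 to 50 points) the product runs from 0.5 to 15 points.

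**4. Would the plan notice?** With 39.4% at home, the standard deviation of that indicator is √(0.394 × 0.606) = 0.489. A 10-point imbalance is then about 0.10/0.489 = 0.20 in standardised units, four times the plan's 0.05 tolerance. It would trigger nothing, because the variable is not in the balance check.

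**The case against.** **Availability.** The list was shortened after a June 2022 survey of what Local Authorities could supply, and only fields held in both arms can be matched on. A reader might infer from the comparison rule that start placement must already be collected in both arms and that the change is only one of wording. The documents do not support that. Table 2 works from end placement, and no listed field in either arm records start placement. Equally, the plan never names it as unavailable. This objection stands, and it makes the fix conditional.

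**Magnitude.** The gaps and imbalances above are assumptions. What counts is the imbalance left after exact matching on child age, domestic abuse and substance misuse, and that is unknown. A reader might also infer that start placement is the strongest predictor of the outcome; the documents give no outcome rate by start placement, so they cannot show this.

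**Sparse strata.** Fourteen exact-match variables, including year and quarter, already divide the sample finely. The cost of a further matching factor in lost FDAC children cannot be estimated from the documents and should not be assumed small. This favours use as a covariate.

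**Timing.** Some sites, London and Kent among those named, give support before proceedings. There, placement at issue may be partly a result of FDAC, and adjusting for it could remove some of the effect.

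**Disclosure.** The plan admits likely selection bias and says matching cannot capture subjective criteria. That admission is general; it does not mention the baseline of the primary outcome.

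**Dropped variables.** A reader might infer that the severity and previous-removal items listed in Appendix C once stood in for start placement. They are parent-level items and do not say where this child was living. The child-level items on orders and previous looked-after status come closer but are only partial, and dropping variables between versions is not in itself a fault.

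**Conclusion.** The point holds as a gap in confounder control, not as a demonstrated bias. By the plan's own criterion, placement at the start of proceedings should be considered for the child-level analysis. It is absent from matching, regression, balance checks and sensitivity analyses, and no reason or limitation is stated for it. The plan is also inconsistent on whether start placement is used to code the outcome, and inconsistent within Outcome measures about a child who returns home.

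The size and direction of any bias cannot be derived from the documents. The 3.3 to 9.0 point range rests on an assumed residual imbalance of 10 to 20 points and an assumed gap of 33 to 45 points. It shows only that plausible values can approach the 9.1 points the study is powered to detect. A reader might infer that the estimate is biased in favour of FDAC; nothing in the documents says which arm has more children at home at issue.

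**What to change.** 1. Reconcile the definition of reunification, the rule comparing end with start placement, and Table 2, so that every start and end combination has one code.
2. State whether placement at issue is held for FDAC and for non-FDAC children.
3. If it is held in both arms, add it (with the primary carer; with the other parent or a relative; in Local Authority care) as a covariate in the primary model, include it in the balance table, and report reunification by start placement in each arm.
4. Match on it only if the loss of FDAC cases stays within the plan's five percent trigger. That is 15 of 300 if counted in children (0.05 × 300), or about 11 of 215 if counted in cases (0.05 × 215 = 10.75).
5. If it is not held in both arms, name its absence as a limitation on the causal claim.
6. Fix the time point as date of issue, and note that at sites giving pre-proceedings support it may be partly affected by FDAC.

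The cost is one more covariate and reliance on a Local Authority field whose availability still has to be confirmed.

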The unit of analysis varies across outcomes. The primary outcome (reunification) is defined at the child-level while secondary outcomes are defined at either the parent-level (i.e. parental substance cessation) or case-level (i.e. contested hearing and the use of expert witnesses). Matching will be implemented separately for outcomes at different units of analysis. Child-level outcomes will include covariates about the child (such as age) and parent characteristics (mainly about primary carer's characteristics such as alcohol and drug misuse at baseline). Parent-level outcomes will include case characteristics (i.e. date of issue) and parent-level covariates (e.g. age, gender, substance misuse, and for how many children they are primary carer).⁶ Case-level outcomes will include case characteristics, including date of issue, aggregated parent-level (e.g. primary carer age, gender, ethnicity) and aggregated child-level characteristics (e.g. how many children in the case).

Comparisons will be made using the original uncoarsened covariates, with differences reported as *Hedges' g* effect sizes. If we observe an imbalance with an effect size of greater than 0.05, we will revise the matching specification by adjusting the coarsening of any variables with an imbalance of greater than 0.05. We will reduce the number of coarsening categories (unless the variable in question is already uncoarsened). If this does not resolve the imbalance, we will coarsen the variable further instead.

We will also use the multivariate L1 distance statistic before and after matching to describe the quality of the matching. This statistic measures the overall imbalance with respect to the joint distribution, including all interactions, of the covariates (Blackwell et al., 2010). The smaller L1, the less the imbalance across the covariates, with L1=0 indicating perfect balance and L1=1 complete separation across covariates.

Data sources and availability

The data to be used for matching and the evaluation of outcomes will be collected from several sources:

- The FDAC data collection tool, for FDAC cases
- Local Authority case management systems, typically within children's social care and legal teams
- Case notes, typically held by Local Authorities and courts

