Data collected as part of the FDAC data collection tool will be the source of data for intervention cases. Ideally, data for the control group would be collected from the same data source, however Local Authorities do not systematically collect all the information collected by FDAC sites. Local Authorities will be asked to provide comparable data from their own case management systems and case notes based on a template developed by NatGen. As far as is possible, we will aim for comparable data collection. For example, we will collect data from fields used in statutory returns, such as those collected in the Children in Need census. Fields collected by control sites will be more limited relative to intervention sites. For

⁵ Although the CONSORT *Statement* was originally developed to guide the reporting of RCTs, many of its components also apply to other types of quasi-experimental impact studies. A flow diagram template will be downloaded from <http://www.consort-statement.org/>.

⁶

example, drug misuse will be based on data collected by Local Authorities, which may not be as accurate as the testing conducted in FDAC sites (e.g. drug testing using samples of parent's hair).

Our data collection template that will be completed by the Local Authorities will include detailed instructions and guidance for all key fields required to complete this evaluation. There will be cell validation in order to minimise blank cells and ensure data comparability across Local Authorities. We will only be able to use fields collected in both FDAC sites and Local Authorities in the matching.

Key characteristics that we intend to include in the matching are illustrated in Table 3. Each of these characteristics are collected in both the FDAC data collection tool and the control group data collection tool. These variables are important indicators of whether a case is suitable for FDAC (such as type of drug and alcohol misuse). However, it cannot account for subjective criteria that may be used by FDAC sites in determining which cases should be supported by FDAC. Table 3 also outlines how specific variables will be coarsened in matching.

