	Ethnicity	Categorical	No coarsening: White, Asian/Asian British, Black African/Black Caribbean/Black British, Mixed/multiple ethnic groups, other, unknown
	Primary carer for how many children	Continuous	Bands: 0 (if not primary carer), 1, 2, 3 or more
	Primary carer – Age of youngest child cared for	Continuous	Age bands: Less than 12 months old, 1, 2-3, 4-7, 8-11, 12-16, N/A (if not primary carer)
	Past experience of domestic abuse	Categorical	No coarsening: Yes – perpetrator, Yes – Victim, Yes – both, No, Unknown
	Currently experiencing domestic abuse	Categorical	No coarsening: Yes – perpetrator, Yes – Victim, Yes – both, No, Unknown
	Whether misusing at time of referral	Categorical	No coarsening: Yes, No, Unknown

	Substance misuse type	Categorical	No coarsening: Drugs, Alcohol, Drugs and Alcohol, None, Unknown
Case-level outcome: contested hearing, the use of expert witness			
Case characteristics	Date of issue	Date	Year and quarter
Parent characteristics aggregated to case level	Number of parents in the case	Continuous	Bands: 1, 2, 3 or more
Parent characteristics	Primary carer – Age	Continuous	Age bands: Less than 18 years old, 18-24, 25-34, 35-44, 45 or older
	Primary carer – Gender	Categorical	No coarsening: Male, Female, Other, Unknown
	Primary carer – Ethnicity	Categorical	No coarsening: White, Asian/Asian British, Black African/Black Caribbean/Black British, Mixed/multiple ethnic groups, other, unknown
	Primary carer – Past experience of domestic abuse	Categorical	No coarsening: Yes – perpetrator, Yes – Victim, Yes – both, No, Unknown
	Primary carer – Currently experiencing domestic abuse	Categorical	No coarsening: Yes – perpetrator, Yes – Victim, Yes – both, No, Unknown
	Primary carer – Whether misusing at time of referral	Categorical	No coarsening: Yes, No, Unknown
	Primary carer – Substance misuse type	Categorical	No coarsening: Drugs, Alcohol, Drugs and Alcohol, None, Unknown
Child characteristics aggregated to case level	Number of children in the case	Continuous	Bands: 1, 2, 3 or more
	Age of youngest child in the case	Continuous	Age bands: Less than 12 months old, 1, 2-3, 4-7, 8-11, 12-16

Table 4. Harmonising FDAC and non-FDAC data			
Derived variable to harmonise available data	FDAC data	Non-FDAC data	How derived

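### The reunification, placement, contested-hearing and expert-witness analyses leave out the other parent's misuse and domestic-abuse status, although the plan intends to hold it in both arms

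*Supplement*

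**What the plan says.** The Identification strategy says that matching needs baseline characteristics linked to selection or to outcome. Its examples are parental misuse and domestic violence in the household. It then narrows the parent covariates: "Child-level outcomes will include covariates about the child (such as age) and parent characteristics (mainly about primary" carer's).

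Table 3 carries this out in three blocks.

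- **Child-level (reunification).** Past and current domestic abuse, misuse at referral and misuse type are all taken from the primary carer, for example "Primary carer – Currently experiencing domestic abuse" and "Primary carer - Substance misuse type". The one item that reflects another parent is "Number of parents in the case", a head-count. The placement model (RQ6) reuses these covariates, according to Additional Analysis.
- **Case-level (contested hearing, expert witnesses).** The same four items again come from the primary carer, for example "Primary carer – Substance misuse type", with the same head-count.
- **Parent-level (cessation).** The same four items are listed for the parent, without the primary-carer restriction. The number of children cared for is coded "Bands: 0 (if not primary carer), 1, 2, 3 or more", and the age of the youngest child has a not-applicable code for parents who are not the primary carer.

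On availability, Data sources and availability says of the Table 3 items: "Each of these characteristics are collected in both the FDAC data collection tool and the control group data collection tool".

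**The concern.** Eligibility (Participants) depends on parental misuse being a key concern in the case. It does not require the misusing parent to be the primary carer. A case can therefore qualify through the other parent while its primary carer is coded No for misuse at referral and None for type. It would then be matched with, and adjusted as, cases that share that coding, and the misuse that brought it into the study would not be seen.

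Whether a second parent is misusing, or has a current role in domestic abuse, could plausibly affect both an FDAC site's decision to take the case and the child's placement. That meets the plan's own test for a matching variable. No reason is given for leaving it out. The resourcing explanation concerns fields removed from the Local Authority template, and these fields were kept for RQ2.

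**Working it through.** **1. Are the fields planned for other parents in both arms?** Four pieces of text bear on this.

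- The parent-level block has a not-applicable code for parents who are not primary carers. The zero band is weaker evidence, because it also appears in the child-level block.
- Secondary Analysis restricts the cessation sample to parents with misuse at baseline. Each parent's baseline status must be known to apply that restriction.
- The cessation model has a case-level random intercept, so more than one parent per case is expected.
- Data sources and availability says that the Table 3 items are held in both tools.

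Together these support the inference, although no sentence states it outright.

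**2. Would another part of the plan catch the omission?** No. The doubly robust estimator protects against misspecifying either the matching or the regression, but both use the same covariate list. Hedges' g (trigger 0.05) and L1 are computed on that list too. The sensitivity analyses change the coarsening or drop the covariates; neither adds any.

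**3. The plan's detectable effect, as a yardstick.** Inputs from Minimum detectable effect size calculations: ICC 0.70; R-squared 0.20 (level one) and 0.10 (level two); 430 cases; 600 children; equal arms; control reunification 25%; two-sided alpha 0.05; power 0.80. R-squared values are placed at the levels given in that section, and the odds ratio uses the exponential conversion.

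- Variance = 0.70 × 0.90 / (0.25 × 430) + 0.30 × 0.80 / (0.25 × 600) = 0.00586 + 0.00160 = 0.00746
- MDES = 2.802 × √0.00746 = 0.242
- OR = exp(0.242 × π/√3) = 1.551
- RRR = 1.551 / (0.75 + 0.25 × 1.551) = 1.363, and 0.25 × 0.363 = 9.1 points

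This reproduces the stated 1.36 and 9.1 points.

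**4. How large could the distortion be?** The documents give none of the inputs, so all are assumptions. Let an adverse other-parent status have prevalence pF in FDAC cases and pC in controls, and let it multiply the chance of reunification by g. With no true effect,

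spurious RR = (1 − pF + pF·g) / (1 − pC + pC·g).

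Take pC = 0.50 to 0.70, an arm difference of 0.10 to 0.20, and g = 0.50 to 0.75.

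- Lowest: pC 0.50, pF 0.40, g 0.75 gives 0.900 / 0.875 = 1.03
- Highest: pC 0.70, pF 0.50, g 0.50 gives 0.750 / 0.650 = 1.15
- Prevalences swapped between arms: 0.875 / 0.900 = 0.97 and 0.650 / 0.750 = 0.87

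A second set of assumptions has a share t = 0.5 to 0.7 of cases with a second parent, who is misusing in 40% of FDAC and 55% to 70% of control two-parent cases. Reunification is 30% without that misuse and 15% to 18% with it.

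- Lowest: (0.30 − 0.5 × 0.12 × 0.40) / (0.30 − 0.5 × 0.12 × 0.55) = 0.276 / 0.267 = 1.03
- Highest: (0.30 − 0.7 × 0.15 × 0.40) / (0.30 − 0.7 × 0.15 × 0.70) = 0.258 / 0.2265 = 1.14

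The implied control rates at these two ends, 26.7% and 22.7%, bracket the plan's 25%.

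Both calculations treat the omitted status as unrelated to the covariates already used. They describe the distortion before adjustment and overstate what remains to the extent that those covariates carry the same information. They cover reunification only; no figure was derived for RQ4, RQ5 or RQ6.

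**5. Why not match on the fields?** Adding all four (3, 5, 5 and 5 levels) as exact-match variables would multiply the possible strata by up to 3 × 5 × 5 × 5 = 375.

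**The case against.** The strongest reply is that centring on the primary carer is deliberate. Under Outcome measures, placement with a different parent does not count as reunification, and the logic model in Appendix A frames the outcome as staying with the same primary carer. That explains why the carer's characteristics come first. It does not make the other parent's status irrelevant to selection or to the court's decision.

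Several further points stand and limit the claim.

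- **Completeness is not stated.** Nothing says how fully Local Authority records hold the other parent's fields, and Unknown is an allowed value. Footnote 6, attached to the parent-level covariates, has no text in the copy reviewed and could not be checked.
- **Partial coverage exists.** Number of parents and the carer's own misuse and abuse role are matched and adjusted. A carer recorded as a current victim already says something about a partner.
- **Measurement differs by arm.** The plan warns that Local Authority drug data may be less accurate than FDAC testing, so adding such a covariate may not remove bias cleanly.
- **The model is already full.** With categories as dummies and continuous items as single terms, the child-level list gives about 37 terms. Expected events are about 150 (25% of 600) to 177 (75 plus 34.1% of 300).
- **Residual selection is disclosed.** The plan concedes likely selection bias. That concession supports adjusting for what is measured; it does not excuse omitting it.

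**Conclusion.** The point holds as an avoidable gap. For RQ1, RQ4, RQ5 and RQ6, a candidate confounder that the plan expects to hold for both arms enters neither the matching, nor the regression, nor the balance checks, and in some cases it is the misuse that made the case eligible. This rests on inferring from the parent-level block and the data-sources text that other parents' fields are collected in both arms.

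The size is illustrative only: a null effect on reunification could show as roughly 1.03 to 1.15, or 0.87 to 0.97 in the other direction, and less after allowing for correlation with covariates already matched.

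Three stronger readings are tempting but unsupported. A reader might infer that the estimates are shown to be biased in FDAC's favour; the documents give no prevalence by arm, so neither the presence nor the direction of bias is established. A reader might infer a loss of precision; nothing in the documents demonstrates one. A reader might extend the point to partner misuse in the RQ2 model; that outcome already uses each parent's own status, and the material here makes no case for the addition.

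**What to change.** Derive two case-level indicators from the parent-level data, in the same way in both arms:

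- (a) any other parent misusing at referral: yes, no, unknown;
- (b) any other parent with a current domestic-abuse role: collapsed categories, with unknown.

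The any-other-parent wording settles cases with three or more parents. Set single-parent cases to the reference level, so that the existing one-parent category carries that information; a separate no-other-parent level would be collinear with it.

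Report both indicators in the balance table, with completeness by arm. Add them as covariates to the RQ1, RQ4, RQ5 and RQ6 models, not as exact-match variables, so that no matches are lost. Show each estimate without them as well. If completeness proves too poor to use them, say so and give that as the reason for exclusion.

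The cost is two derived variables and a few model terms: four if both are coded in three levels, taking the child-level list from about 37 to 41. No new data collection is needed. Some terms may be sparse and recording accuracy may differ between arms, which is why the estimate without them should stand alongside.
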